There are two subject types in this study – ED clinicians and ED patients. ED clinicians (attending physicians and physician assistants) will be recruited to train in and administer the proposed intervention on ED patients. After the intervention is administered, they will be asked to complete a Likert scale survey about acceptability. Clinicians will be asked to participate voluntarily. The PI will make an announcement at the faculty / physician assistant meetings and hand out the study information sheet. ED patients will be recruited to be interviewed after the intervention to learn their perception of the intervention. Upon identification of the

potential subject, the trained RAs will approach the potential subject to explain the study and ask about their willingness to participate. Once the eligible subject agrees to participate, the PI will consent the patient to enroll. After the trained RAs explain the study, the subjects will have time to think about the enrollment until the PI physically arrives in the ED. The PI will review all study elements again with the subjects to ensure understanding of the study. Upon enrollment, the trained physician responsible for the care of the patient will administer the intervention. When a trained physician is not on duty in the ED observation unit, the PI will administer the intervention.

There will be no other methods of recruiting for this study. Since this is a single-armed, pre-/post-intervention assessment study, there will be no treatment assignment or randomization.

V. STUDY PROCEDURES

There will be two distinct parts of the study: acceptability study (Part I) using qualitative interviews to explore the patient’s perception of the intervention and quantitative assessment of clinician’s acceptability rating, and feasibility study to measure patient-reported outcomes (Part II) after leaving the ED for future randomized clinical trial. The timing of proposed data collection is shown on Table 3.

| Table 3 Timing of Proposed Data Collection and Instruments | | | | |
|------------------------------------------------------------|------------|--------------------------------------------------------|-----------------------|--------------------------------------------------------|
| Study Part | Subjects | Pre-Intervention | Post-Intervention | Three Month Follow-up |
| Part 1 | Clinicians | | Acceptability Survey | |
| | Patients | | Qualitative Interview | |

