We will collect pre-/post-intervention data to demonstrate the intervention's feasibility to improve patient-reported outcomes. We will measure patient-reported outcomes before (in-person) and three months after our intervention (over the phone). We will assess the proportion of participating older adults who self-reported having spoken to their primary outpatient physician and/or caregivers about their goals for end-of-life medical care following the intervention. We will use validated instruments to measure quality of life (QUAL-E),¹³ ACP engagement behavior (ACP Engagement Survey),¹⁴ patient empowerment (Patient Activation Measure – PAM™),¹⁵ and potential subjective distress caused by the intervention (a potentially traumatic event).¹⁶

Measurements

We will measure the proportion of patients who self-report having had the conversation with their outpatient physician. We will also use QUAL-E, a validated instrument to measure quality of life of patients with a range of diseases (cancer, congestive heart failure, chronic obstructive pulmonary disease, and end-stage renal disease).¹³ This instrument is particularly suited to measuring the quality of life of patients who may or may not have acknowledged the terminal nature of their disease, but who, nevertheless, are dealing with end-of-life issues. In addition, we will use the ACP Engagement Survey, a validated instrument developed based on Social and Behavior Change Theory, and it measures the full range of self-reported processes involved in ACP (e.g. changes in knowledge, contemplation, self-efficacy and readiness) as well as actions associated with ACP behavior.¹⁴ We will also use the PAM™, which is a validated instrument that measures the four stages of patient empowerment: (1) believing the patient role is important, (2) having the confidence and knowledge necessary to take action, (3) taking action to maintain and improve one's health, and (4) staying the course even under stress.¹⁵ To evaluate whether the ED intervention itself increases patient stress, we will also measure posttraumatic stress disorder symptoms using the Impact of Event Scale – Revised (IES-R).¹⁶ IES-R is a validated scale to assess subjective distress caused by traumatic events. The trained RAs will administer these instruments (see *Appendix*)

immediately before the intervention, and again by phone three months later. IES-R will only be used at three month.

Outcomes

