The primary outcome is the proportion of patients self-reporting having spoken to their primary outpatient physician regarding their preferences for end-of-life medical care three months after the ED intervention. The secondary outcomes are quality of life, ACP behavior change, PAM™, posttraumatic stress disorder symptoms, proportion of subjects with documented ACP conversation on medical records three months after the intervention. We will also track the rate of patients being lost-to-follow-up to aid in appropriate design of a future randomized clinical trial.

VI. BIostatistical Analysis

Variables to be collected

We will collect demographic information of our subjects from the electronic health records, including age, gender, prior ACP documentation, co-morbid medical conditions, and ED diagnosis. Both the administration of BMI intervention by a clinician and subsequent qualitative interview of the participants will be video-recorded to ensure fidelity of the intervention administration and accurate capturing of their inputs. We will also administer the validated survey instruments (ACP Engagement Survey, QUAL-E, PAM™, IES-R) and self-reported completion of ACP conversation three months after leaving the ED.

Study Endpoint

Part I – Acceptability Study

The study will conclude when 15 to 25 participants are enrolled and thematic saturation of the qualitative analysis is reached.

Part II – Feasibility Study

The study will conclude when 100 participants are enrolled and three month post intervention data is collected over the phone.

Statistical Methods

Part I Analysis

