We will employ a modified phenomenological approach to code for themes that illustrate patient's perception of the intervention. We selected phenomenology as our qualitative research strategy since it is particularly suited to explore how individuals experienced our intervention. The PI and the trained RA will immerse themselves in the text by reading and re-reading for content, quality, and patterns. During this time, the audit trail of notes will be kept by individual coders to be reviewed in a subsequent discussion group. After independent coding of 5 initial transcripts, the PI and the trained RA will determine the standard labeling for common patient perception themes; and these will be organized into a code book. We will iteratively re-organize the code book until the consensus is reached among the coders. If there are disagreements between the coders on a particular theme, we will employ a third coder to aid in judgment of the codes. The coders are

purposefully not blinded to the study questions because they need to decide what is pertinent to answer the study question at hand. The coders will use the code book to independently code the remaining transcripts. We will use Nvivo software to organize and manage our data. The study will conclude when new themes no longer emerge (thematic saturation is reached), based on agreement between the coders. If not, we will continue to recruit more subjects until thematic saturation is reached. The themes will be categorized and coders will decide with group consensus which quotes will be included as the representative quotes in the final manuscript. If there are disagreements, an additional researcher from the ED will be asked to review the quotes and themes.

Part II Analysis

We will calculate descriptive statistics of the patient-reported outcomes before and after the intervention. We will use one sample binomial exact test of proportions for categorical outcomes (e.g. proportion of patients reporting ACP conversations with their physicians), and Wilcoxon signed ranks test for ordinal outcomes (e.g. QUAL-E) at baseline and three months. We will use a p-value of 0.05 as the significance threshold.

Sample Size

Part I:

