We propose to enroll 10 to 25 subjects in Part I ~~this pilot study~~. In prior qualitative studies, this is the general number that a study like this takes to reach thematic saturation. We may enroll more than 25 subjects if we find that thematic saturation has not reached. We will submit an amendment to change the enrollment number should that occur.

Part II:

We propose to enroll 100 subjects in Part II. A recent meta-analysis of advance directive documentation studies demonstrated improvement in ACP completion rate ranging from 2 to 44% with an intervention.¹⁷ We assume that the baseline rate of ACP completion rate is <10% to be conservative. Base on prior similar studies, we assume our intervention will result in 25% increase in the rate of conversation above 10%. A sample of 100 subjects will afford us 97% power (two-tailed alpha of 0.05) to detect a difference of the conversation completion rates of 10% before the intervention versus 30% after the intervention. Power is also expected to be strong for the ACP behavioral change scale outcomes (our secondary outcome, similar preliminary data demonstrated a pre-to-post improvement of 0.5 SD).¹⁸ With a conservative assumption, we will have 85–98% power with our sample size.

VII. RISKS AND DISCOMFORTS

There is no risks and discomforts associated with procedures, drugs, devices, or radiation in this study.

Psychosocial Risks (Uncommon)

The participants will be introduced or re-initiated on the topic of ACP. Some patients with serious illness do not wish to discuss ACP because they feel uncomfortable with the topic. This potential discomfort, however, is a part of the

routine practice of EM. Many ED clinicians discuss ACP with patients routinely, and the study does not add additional discomfort that is different from the routine clinical practice. Further, PI is trained in serious illness communication and will be available to manage patients' anxiety and other emotions as needed.

VIII. POTENTIAL BENEFITS

Potential Benefits to Participating Individuals

It is our hope that the proposed intervention will empower patients to engage in ACP discussions with their primary outpatient clinician $\geq 25\%$ of the time three months after the ED visit. Further, this intervention may also improve other patient-reported outcomes without causing significant harm.

Potential Benefits to Society

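### The one-sample test named for the primary conversation outcome does not make the 10% before versus 30% after comparison the study is powered for, and 97% is not its power

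*Protocol*

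**What the plan says.** - **Test.** Protocol VI, Part II Analysis: "We will use one sample binomial exact test of proportions for categorical outcomes (e.g. proportion of patients reporting ACP conversations with their physicians". No null proportion is given. The same sentence assigns the Wilcoxon signed ranks test to ordinal outcomes and ends by referring to baseline and three months.
- **Design.** Protocol IV: "Since this is a single-armed, pre-/post-intervention assessment study, there will be no treatment assignment or randomization".
- **Power.** Protocol VI, Sample Size, Part II, claims: "A sample of 100 subjects will afford us 97% power (two-tailed alpha of 0.05". The effect to which this power belongs is worded there as follows: "to detect a difference of the conversation completion rates of 10% before the intervention versus 30% after the intervention". The test behind this figure is not named.
- **Source of the 10%.** Same section: "We assume that the baseline rate of ACP completion rate is <10% to be conservative". It is an assumption, not a measured rate.
- **Collection of the outcome.** Protocol V, Part II: "We will measure patient-reported outcomes before (in-person) and three months after our intervention (over the phone"). Part II Analysis: "We will calculate descriptive statistics of the patient-reported outcomes before and after the intervention". The list of variables in VI, however, has only "self-reported completion of ACP conversation three months after leaving the ED", and Table 3 shows no separate conversation item at either time.
- **Target.** Hypothesis (c) in II expects at least 25% of participants to report the conversation at three months.

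**The concern.** The analysis section and the sample size section describe different comparisons for the same primary outcome. A one-sample exact test asks whether the three-month proportion differs from a fixed number. A before/after comparison in the same patients is paired and needs each patient's baseline answer. The Protocol uses a paired test for its ordinal outcomes but not for its primary one.

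A three-month proportion set against a reference rate can be a valid analysis of a single-arm pilot. The risk lies in the mixture. A p-value below 0.05 could be reported as an increase after the intervention when it shows only that the three-month rate exceeds an assumed constant. The results are meant to inform the design of a randomised trial, so that misreading would carry forward. The stated power does not help the reader tell which analysis was intended.

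**Working it through.** **Inputs from the Protocol.** n = 100; two-sided alpha 0.05; 10% before, 30% after; stated power 97%; target at least 25%.

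**Assumptions, because the Protocol gives no figure.** True background conversation rates of 8% to 25%; 70 evaluable patients at three months; for paired tests, the share of patients who switch from yes to no (reverse discordance).

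**1. Can the 97% be reproduced with the named test?** Let X be the number reporting a conversation, X ~ Bin(100, p), with null p0 = 0.10. The two-sided exact p-value is 0.064 at X = 16 and 0.028 at X = 17, so the test rejects upward at X ≥ 17.

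- Power at p = 0.30: P(X ≥ 17) = 0.999.
- Power at p = 0.25: P(X ≥ 17) = 0.979.

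The named test therefore has 99.9% power for the stated rates. It already reaches 97.1% with 56 patients (critical value 11). It comes near 97% at n = 100 only if the true rate is 25%, not 30%.

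**2. Is 97% the power of a paired test?** With reverse discordance b, a rise from 10% to 30% implies 0.20 + b switching from no to yes. Given m discordant pairs, exact McNemar tests the number of no-to-yes switches against Bin(m, 0.5). Power is averaged over m ~ Bin(n, 0.20 + 2b).

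| b (assumed) | n = 100 | n = 70 |
|---|---|---|
| 0.01 | 99.9% | 97.9% |
| 0.03 | 98.6% | 92.5% |
| 0.05 | 96.1% | 86.3% |
| 0.07 (independent answers: 0.10 × 0.70) | 92.9% | 79.9% |

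At n = 100 this equals 97.0% only at b = 0.044, which the Protocol does not state. The 97% therefore does not identify the intended test.

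**3. What does the one-sample test do with no intervention effect?** Here the three-month rate equals the background rate. The probability of a significant increase is P(X ≥ 17) at n = 100, or P(X ≥ 13) at 70 evaluable.

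| True background (assumed) | n = 100 | n = 70 |
|---|---|---|
| 8% | 0.2% | 0.3% |
| 10% | 2% | 2% |
| 12% | 9% | 7% |
| 15% | 33% | 24% |
| 20% | 81% | 66% |

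**4. How does exact McNemar compare (n = 100)?**

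- Stable background of 10%, 15%, 20% or 25%, independent answers: false significant increase 1.5%, 1.5%, 1.6%, 1.7%.
- Background drifting from 10% to 20% with no intervention effect: 42% with independent answers, and 54%, 66% and 83% at reverse discordance 5%, 3% and 1%. The one-sample test gives 81%.

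The paired test protects against a stable background above 10%. It does not protect against drift.

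**5. Significance against the Protocol's own target.** Results of 17 to 24 out of 100 would be significant against 10% yet miss the 25% target. The exact 95% CI is 10.2% to 25.8% for 17/100 and 16.9% to 34.7% for 25/100.

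**The case against.** The one-sample test fits the endpoint as defined. The primary outcome is a proportion at three months, and hypothesis (c) is an absolute three-month rate. On that reading only the before/after phrase in the sample size section is loose, 10% is the evident null, and its formal statement could be left to a SAP. The power error is also harmless, since the true figure is higher than the stated one. This largely stands: the test is usable and n = 100 is adequate. But the Protocol itself fixes a test, a comparison and a power figure that disagree, so this is not an omission that a SAP may fill.

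The sentence naming the test ends by mentioning both time points, and exact McNemar is itself a binomial test on discordant pairs. A paired test might therefore have been meant. The wording points to a simple test of one proportion, however, and discordant pairs are mentioned nowhere.

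The ACP Engagement Survey, given at both times, covers ACP actions and may already contain a baseline conversation item. That is possible, but the Protocol does not say that the primary outcome comes from it.

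The 33% and 81% depend on background rates that the Protocol does not give, and excluding patients with clearly documented goals may keep the background low. That is correct: below 10%, the test rejects upward about 2% of the time or less. McNemar also has no control group and fails under drift, so it is one of two acceptable repairs, not a cure.

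**Conclusion.** The concern holds. The named test does not make the powered comparison, its null is not stated, and its power for 10% versus 30% with 100 patients is 99.9%, not 97%. Those points follow from the Protocol's own figures, taking its 10% as the null.

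The practical size depends on the unmeasured background rate: negligible if it is below 10%, and 33% to 81% false declarations of an increase if it is 15% to 20%. Those rates are assumptions. The sample size need not change for the one-sample test. For a paired test the power depends on discordance and follow-up, neither of which the Protocol specifies. This should be fixed before analysis: it concerns the Part II primary outcome and the repair is cheap.

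**What to change.** Choose one of two routes and make the analysis, sample size and data collection sections agree.

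**Paired route.**
- State that the same conversation item is asked at the existing pre-intervention visit with a three-month look-back, or name the ACP Engagement Survey item if it already covers this.
- Compare baseline with three months by exact McNemar, and report the paired difference with its 95% CI.
- Restate the power with the assumed discordance and follow-up.
- Say that the comparison removes only a stable background, not effects of time, illness course or the ED visit.

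**One-sample route.**
- Name the null and its source.
- Replace the before/after wording with reference rate versus three-month rate.
- Restate the power for 10% versus 30% as 99.9% at n = 100 (99% if 70 are evaluable).

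Under either route, report the three-month proportion with its exact 95% CI against the 25% target; under the one-sample route, lead with it.

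**Cost.** The paired route needs wording and at most one question at a visit that already takes place. Its power is about 93% to 99.9% at n = 100 and 80% to 98% at 70 evaluable, for assumed reverse discordance of 7% down to 1%. The one-sample route costs wording only.

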Detailed Protocol

Title: A pilot study to test the acceptability and feasibility of brief motivational interview intervention to help patients formulate their goals for medical care in the emergency department

Principal Investigator: [name], MPH

Funding: Emergency Medicine Foundation Career Development Award

Version Date: 5/12/2017

[figure not shown]
I. BACKGROUND AND SIGNIFICANCE

The majority (75%) of older adults with serious illnesses visit the ED during the last six months of life.¹ ED visits often mark an inflection point in these patients' illness trajectories, signaling a more rapid rate of decline.^{2,3} Many of these patients have not formulated and communicated their goals for end-of-life care,⁴ and the majority (56 to 99%) of older patients do not have advance directives available at the time of ED presentation.⁵ Most of these patients have priorities other than simply to live as long as possible,⁶ yet without alternative plans in place, they may receive aggressive care that does not align with their goals.⁷ Therefore, the ED provides a point in time and a location to identify and empower patients who would benefit from formulating and communicating their goals for future medical care.

Emergency medicine (EM) physicians recognize this opportunity and have expressed interest in engaging older adults with serious illnesses in a discussion of their end-of-life care;⁸ however, the time-pressured ED environment discourages physicians from conducting in-depth conversations with these patients.⁴ There is not yet a suitable brief intervention that is acceptable in the ED environment for physicians without extensive training in serious illness communication. Lack of a feasible method to intervene in the ED constrains our current clinical practice.

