Test the acceptability and feasibility of our brief motivational interview intervention to facilitate advance care planning (ACP) conversation on older adults with serious co-morbid illness being discharged from the emergency department (ED) and interview the participants to understand their perception and collect patient-reported outcomes data after leaving the ED.

Hypotheses

- a) $\geq 80\%$ of clinicians will find it acceptable to conduct this interview in the ED for appropriate patients;
- b) $\geq 80\%$ of patients will find the interview respectful to patient-oriented needs;
- c) $\geq 25\%$ of participants will have reported completing ACP conversation with their primary outpatient clinician at three month after leaving the ED.

Methodology

We will pilot test (Part I) the intervention to ED patients and interview 15 to 25 participants (depending on theme saturation) immediately following the intervention to explore how they perceived the intervention. After the intervention is administered, they will be asked to complete a Likert scale survey about acceptability. Additionally, we will collect pre-/post-intervention patient-centered outcome data (Part II) in-person at the time of intervention and via phone interview at three months after the ED visit for 100 patients.

III. SUBJECT SELECTION

Trained RAs will recruit the subjects using the inclusion and exclusion criteria (**Table 2**). We will use convenience sampling for this study. Each morning when a trained EM physician evaluates patients in the ED observation unit, the trained RAs will ask the physician to identify potential subjects based on inclusion and exclusion criteria.

| Inclusion | Exclusion |
|-------------------------------|--------------------------------------------------|
| ≥ 65 years of age | Acute physical or emotional distress |
| English-speaking | Determined by EM physician not to be appropriate |
| Capacity to consent | Clearly documented goals for medical care** |
| AND ≥ 1 Serious illness* | Already enrolled in this study |

*New York Heart Association stage 3 or 4 heart failure, oxygen-dependent chronic obstructive lung disease, chronic kidney disease on dialysis, and metastatic cancer. **MOLST, medical order for life sustaining treatment.

IV. SUBJECT ENROLLMENT

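### The Part II sample size calls an unsourced baseline of under 10% conservative, but a low baseline is the favourable assumption, and in a single-arm study a rate above 10% does not by itself show an effect

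*Protocol*

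**What the plan says.** The sample size text for Part II (Protocol, Section VI) sets the baseline with the words "We assume that the baseline rate of ACP completion rate is <10% to be conservative". It then claims 97% power with 100 subjects at a two-sided alpha of 0.05 "to detect a difference of the conversation completion rates of 10% before the intervention versus 30% after the intervention". No source is attached to the baseline.

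The Part II analysis names the test: "We will use one sample binomial exact test of proportions for categorical outcomes". Its example is the proportion of patients reporting the conversation. It does not give the null value.

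Section IV describes a single-arm study without randomization. The primary outcome in Section V is self-reported: whether the patient has spoken with the primary outpatient physician about end-of-life preferences by three months.

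Two other places bear on the baseline. Section I reports that "the majority (56 to 99%) of older patients do not have advance directives available at the time of ED presentation". Table 2 in Section III excludes patients with "Clearly documented goals for medical care", which its footnote ties to a MOLST order.

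**The concern.** An assumption is conservative if being wrong about it in the likely direction would not flatter the study. Here the opposite holds. If more than 10% of these patients would report a conversation at three months anyway, two things follow. A follow-up rate of 30% represents a smaller gain than planned. And a test against 10% can be significant although the intervention did nothing.

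The second consequence matters more. With no control arm, the reference value carries the whole inference. The pilot is meant to inform a later randomized trial, so a background rate mistaken for an effect would pass into that trial's planning.

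**Working it through.** **Inputs.** From the protocol: n = 100, two-sided alpha 0.05, 10% before and 30% after, one-sample exact binomial test, single arm. Assumed here: the null is 10% (the only reference value given), all 100 patients have a three-month answer, and the background rate is 15%, 20% or 25%. Background rate means the share who would report a conversation at three months without the intervention. The protocol gives no figure for it.

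**Rejection region.** With X ~ Binomial(100, p0), reject upward at the smallest r with P(X ≥ r) ≤ 0.025, and downward at the largest l with P(X ≤ l) ≤ 0.025. For p0 = 0.10:

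- P(X ≥ 16) = 0.040 and P(X ≥ 17) = 0.021, so r = 17.
- P(X ≤ 5) = 0.058 and P(X ≤ 4) = 0.024, so l = 4.
- The two-sided size is 0.021 + 0.024, or 4.4% from the unrounded values.

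**The plan's own figure.** Power at a true rate of 30% is P(X ≥ 17 | 0.30) = 99.9%. The stated 97% is therefore not what the planned test gives. A paired McNemar test gives 94.1% with independent responses and 99.8% with no reversals, so some unstated discordance in between would give 97%. The protocol does not say how 97% was obtained.

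**Significant result with no effect.** The null stays at 10% and the true three-month rate equals the background rate:

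| True background rate | Chance of rejecting 10% |
|---|---|
| 10% | 4.4% (2.1% in the upper tail) |
| 15% | 33% |
| 20% | 81% |
| 25% | 98% |

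For 15% and above, essentially all of this lies in the upper tail, so it would be read as improvement.

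**Power if the follow-up rate is 30% and the null is set at the baseline:**

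| Baseline | Reject upward at | Power |
|---|---|---|
| 10% | 17 | 99.9% |
| 15% | 23 | 95.2% |
| 20% | 29 | 62.3% |

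**Power if the gain is fixed at 20 points, same test:**

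| Baseline → follow-up | Power |
|---|---|
| 10% → 30% | 99.9% |
| 20% → 40% | 99.2% |
| 30% → 50% | 98.2% |
| 40% → 60% | 97.3% |
| 44% → 64% | 97.5% |

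The direction is the same in both power tables: 10% gives the highest power. The size differs. The loss is large when the follow-up rate is held at 30% and small when the gain is held at 20 points.

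**The case against.** **The word has a defensible reading.** The assumption is a rate below 10%, and the power statement uses 10%, the top of that range. Within the range this is the least favourable value: for a 20-point gain, power is 99.99% from 5% and 99.9% from 10%. This stands, but only inside the assumed range. It says nothing about rates above 10%, which is where the risk lies.

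**A reader might infer that the protocol contradicts itself**, because Section I reports 56 to 99%. It does not. That is the share without an advance directive available, so the share with one is 100 − 99 = 1% to 100 − 56 = 44%, which includes values below 10%. It also counts documents at hand in the emergency department, whereas the outcome is a conversation with the outpatient physician. The MOLST exclusion may lower the rate among those enrolled. The figure neither refutes nor supports the baseline. Equally, nothing in the protocol rules out a background conversation rate above 10%. The exclusion's footnote names only MOLST, and Section VI plans to collect prior ACP documentation on those enrolled.

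**A reader might also infer that the stated 97% is a best case.** The planned test does not support that. It gives 99.9% under the stated inputs and about 97% or more for a 20-point gain at every baseline checked up to 44%. A two-sample formula would show a steeper fall, but it assumes two independent groups of 100, which this design does not have.

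**The null of 10% is inferred**, and the single-arm design is openly stated. Both are true. If another null was intended, the chances of rejection without an effect would change, and the protocol should name that value.

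**Conclusion.** The point holds in limited form. The baseline is unsourced, and calling it conservative is wrong for any rate above 10%. The main consequence concerns interpretation: if 10% is the null, a significant three-month result is likely without any effect once the background rate reaches about 20% (81%), and is far from rare at 15% (33%). Loss of power is a real concern only if the follow-up rate stays near 30% while the baseline is higher, where power falls to 62% at a 20% baseline.

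These figures rest on the inferred null, complete follow-up of 100 patients and assumed background rates. They show what the design cannot distinguish. They do not show that the true background rate exceeds 10%.

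**What to change.** In the Part II sample size text:

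1. Delete the claim that the baseline is conservative, and call 10% an assumed reference value.
2. State 10% as the null of the one-sample exact test, here and in the Part II analysis.
3. Report power from that test for a 30% three-month rate at baselines of 10%, 15% and 20%: 99.9%, 95% and 62%.
4. State that a three-month rate significantly above 10% is not by itself evidence that the intervention raised the rate, because there is no control arm and the background rate is not known.

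The cost is a few sentences. Sample size, procedures and data collection do not change. What the protocol gives up is the appearance of a safety margin and a stronger conclusion than a single-arm pilot can support.

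### The 97% power stated for 10% versus 30% in Part II does not follow from the one-sample exact test the protocol names (99.9% against a fixed 10%), and the assumed increase does not lead to 30%

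*Protocol*

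**What the plan says.** The statements that bear on the power of the Part II primary outcome are these.

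- Protocol VI, Sample Size, Part II, on enrolment: "We propose to enroll 100 subjects in Part II".
- Same paragraph, on the reference rate: "We assume that the baseline rate of ACP completion rate is <10% to be conservative".
- Same paragraph, on the assumed effect: "we assume our intervention will result in 25% increase in the rate of conversation above 10" (per cent).
- Same paragraph, on power: "A sample of 100 subjects will afford us 97% power (two-tailed alpha of 0.05) to detect a difference", the difference being between "conversation completion rates of 10% before the intervention versus 30% after the intervention". The sentence names no test and makes no allowance for dropout.
- Protocol VI, Part II Analysis: "We will use one sample binomial exact test of proportions for categorical outcomes". The example given there is the proportion reporting an advance care planning (ACP) conversation. The significance threshold is 0.05, and no null value is given for the test.
- Protocol VI, Variables to be collected, lists "self-reported completion of ACP conversation three months after leaving the ED".
- Protocol II, hypothesis (c), sets at least 25% as the share "of participants will have reported completing ACP conversation with their primary outpatient clinician at three month after leaving the ED".
- Protocol V, Part II Outcomes, says that loss to follow-up will be tracked.

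**The concern.** The protocol gives everything needed to recompute the power: sample size, alpha, sidedness, two rates and, one subsection earlier, a test. Put together, they do not return the printed figure. The power sentence speaks of before and after, which suggests a paired comparison. The named test is a one-sample test, and the self-report is listed only at three months, which suggests comparison with a fixed rate.

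The effect size is also unclear. Two adjacent sentences describe it differently, and nothing connects them. The reader cannot tell which three-month rate the study is powered for. The study is meant to inform the design of a later randomised trial, so an effect size and power basis that cannot be traced may be carried forward.

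**Working it through.** **Inputs from the Protocol.** n = 100; two-sided alpha = 0.05; reference rate p0 = 0.10; rate in the power sentence p1 = 0.30 (all from VI, Sample Size, Part II). Test: one-sample exact binomial (VI, Part II Analysis). **Assumption:** p0 = 0.10 is the fixed null.

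**1. The stated figure under the named test.** Let X be the number of 100 patients reporting a conversation. The upper limit is the smallest c with P(X ≥ c | 0.10) ≤ 0.025, and the lower limit is the largest d with P(X ≤ d | 0.10) ≤ 0.025.

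- P(X ≥ 17 | 0.10) = 0.0206, while P(X ≥ 16 | 0.10) = 0.0399, so c = 17.
- P(X ≤ 4 | 0.10) = 0.0237, while P(X ≤ 5 | 0.10) = 0.0576, so d = 4.
- Exact size = 0.0206 + 0.0237 = 0.0443. Ordering outcomes by their probability gives the same rejection region.
- Power = P(X ≥ 17 | p1) + P(X ≤ 4 | p1).

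| Three-month rate | Power, n = 100 |
|---|---|
| 12.5% | 11.9% |
| 25% | 97.9% |
| 30% | 99.9% |
| 35% | >99.9% |

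The stated 97% is not reproduced at 30%: the difference is 99.9 − 97 = 2.9 percentage points. The one-sample normal approximation also gives 99.9%. The exact test has 97% power at a rate of about 24.3%, which appears nowhere in the protocol.

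**2. What would give about 97% at 10% versus 30%.**

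*Fewer evaluable patients.* The same exact test with its limits recomputed:

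| Evaluable | Reject at | Power at 30% | Power at 25% |
|---|---|---|---|
| 100 | ≤4 or ≥17 | 99.9% | 97.9% |
| 80 | ≤2 or ≥15 | 99.2% | 92.6% |
| 60 | ≤1 or ≥12 | 97.1% | 85.2% |

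*A paired test.* For the exact McNemar test with 100 pairs, let b be the share changing from yes to no. The share changing from no to yes is then b + 0.20. Power is averaged over the binomial number of discordant pairs.

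| b | Exact McNemar power |
|---|---|
| 3% | 98.6% |
| 4% | 97.5% |
| 5% | 96.1% |
| 7% (independent answers, 0.10 × 0.70) | 92.9% |

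*Two independent groups of 100.* The pooled two-sided z test gives 94.8% and its one-sided version 97.5%. Neither fits a single-arm study with a two-tailed alpha.

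Each of these routes needs a number or a test that the protocol does not state.

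**3. The assumed increase.** Read as absolute, 10% + 25% = 35%. Read as relative, 10% × 1.25 = 12.5%. Neither is the 30% in the next sentence.

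**The case against.** The strongest objection is that the protocol never calls 10% the null of the exact test. It is an assumed baseline. Exact McNemar is itself a one-sample exact binomial test on the discordant pairs, and the study is described as pre/post. On that reading 97% is attainable at about 4% yes-to-no change. This part stands: the 97% must not be called arithmetically impossible. But the 4% is stated nowhere, McNemar is not named, and the self-report is listed only at three months. With 10% the only reference rate given, a fixed null of 10% is the plainer reading. On either reading the figure cannot be traced from what is written.

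A reader might infer that the study is underpowered. The document does not support that. For 10% versus 30% the named test has more power than is printed, and 100 patients give at least 92.9% under the one-sample test and under the paired test with up to 7% changing from yes to no. The 11.9% at 12.5% shows only how much the loose wording leaves open. Nothing indicates that the sponsor meant a relative rise, and the power sentence itself uses 30%.

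A reader might also infer that the 25% in hypothesis (c) contradicts the 30%. It need not, because a hypothesised success level and the alternative used for power can differ. Likewise, powering at 30% when 35% is expected could be a deliberate margin. The text does not say so, and such a margin would not turn 99.9% into 97%.

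**Conclusion.** The point holds as a minor error in a stated figure. With 100 evaluable patients and 10% as the fixed null, the named test has 99.9% power at 30%, against 97% printed, and the described increase leads to 35% or 12.5% rather than 30%. The conclusion depends on taking the 10% baseline as the null. If a paired test was intended, the error lies instead in the named test and in the missing discordance assumption.

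For 10% versus 30% the error is conservative, so enrolment of 100 is not called into question. The 99.9% also assumes that all 100 patients give three-month data. The protocol expects some loss to follow-up, so that figure should not be printed without the condition.

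**What to change.** 1. In Sample Size, Part II, replace the 25% increase with one absolute three-month target rate, and use that rate in the power sentence.
2. State that the power is for the one-sample exact binomial test against a fixed null of 10%. Replace 97% with that test's power for a stated number evaluable. At 30% this is 99.9% with 100 patients, 99.2% with 80 and 97.1% with 60. At 25% it is 97.9%, 92.6% and 85.2%.

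These two changes are text only and add no patients.

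If a paired before/after comparison was intended, replace step 2 as follows. Name that test for this outcome in the Part II Analysis, and state the assumed yes-to-no share with its power (for 10% versus 30% with 100 complete pairs, 97.5% at 4% and 92.9% at 7%). Confirm also that the same question is asked at baseline. Neither Table 3 nor the list of variables shows a separate baseline self-report item. The ACP Engagement Survey given at baseline covers ACP actions, but nothing says that it supplies this outcome. The paired option may therefore need one added baseline item, so it is not purely a text change.
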